14.0 BIOSTATISTICS

This is a blinded randomized control trial to compare the efficacy of a four week treatment with the rifaximin versus placebo in the management of Anterior Resection Syndrome (ARS) following Sphincter Preserving Surgery (SPS) for low rectal cancers. Patients will be randomized into 2 groups, one to receive rifaximin 400mg bid for 4 weeks and one group to receive a placebo bid for 4 weeks.

The primary endpoint is the change in the MSKCC bowel function index from baseline to 4 weeks after the start of therapy. At 4 weeks the patients will have been on therapy for 4 consecutive weeks. The MSKCC bowel function index has been validated to examine 4 week changes in the bowel function. [5] It consists of 18 items to which patients respond using a 5-point Likert scale, ranging from Always to Never. There is a summary score, and three subscales with good internal consistency (Frequency ($\alpha=0.75$), Dietary ($\alpha=0.78$), Urgency ($\alpha=0.79$)) and test-retest reliability (total score =0.84, Frequency=0.74, Dietary=0.62, Urgency=0.87). Each subscale is scored by summing up the responses to the items in the subscale. If there are missing items within a subscale, the mean of the completed subscale items will be substituted for the item when >50 percent of the items in the subscale is completed. A global score will be calculated by adding the subscale scores. An additional aggregate score (total score) will also be calculated with the subscales and the single items. A subscale will be considered missing if more than one-half of the items are missing. The global score will be considered missing if any of the subscales or single items were missing. The average total score (frequency, urgency, dietary, plus four single items) among the 129 MSKCC rectal patients following SPS used to develop the bowel function index was 63.7 with standard deviation of 11.6 and range of 35 – 83. Larger BFI scores indicate better function. In this study the main comparison of interest is to examine whether the change in global-BFI from baseline to 4 weeks after four weeks of rifaximin is different from the change from baseline to 4 weeks of placebo. The analysis will be done using an ANCOVA model, with baseline BFI and treatment indicator as covariates and 4 week BFI as the dependent variable.

Based on clinical observation, we expect the difference in BFI between the two treatments to be fairly large. We would like to accrue 30 patients in each arm stratified by surgical procedure (hand sewn versus stapled anastomosis) for randomization to ensure the two arms are balanced, as surgical procedure is known to correlate with BFI.

Power calculations are based on the global score on the BFI. Based on [name] work when developing the BFI score in 129 MSKCC rectal cancer patients, the lowest mean BFI score was found among the hand sewn patients. The mean BFI score for these patients was 42 with a standard deviation of 8 and 51.6 with a standard deviation of 9 among patients with stapled anastomosis. In a current prospective study of 225 patients which is still maturing, we have found that at 6 months, the BFI discriminates between many clinical parameters with one of the most significant predictors being hand sewn vs stapled anastomosis (a surrogate for tumor level) (Mean 43.3, std 7 (n=36) vs Mean 49.4, std 8 (n=81). Based on these data, we anticipate that a difference of 6 points on the BFI is clinically and statistically meaningful.

For our power calculation, we set the type I error at 5%. We assume that the placebo arm will have no change in BFI from baseline to 4 weeks after the start of therapy. We also assume that the baseline for both treatment groups will be on a similar

magnitude. In line with the above average scores and standard deviations in [name] past and ongoing studies, we assume that the standard deviation of the differences to be 8 and the average BFI score at baseline to be 44. Using a two-sided, two sample t-test, we will have 80% power to detect a difference of differences from 0 in the placebo arm to 5.8 in the rifaximin arm with 30 patients in each arm. We expect to accrue the 60 patients for this study in 1 year, with a plan to recruit 35 in each arm to account for dropout.

In secondary analyses, we will examine the change in BFI scores adjusted for possible cofounders, such as peri-op radiotherapy. We will also examine bowel function data from the weekly logs in order to learn in what time frame (onset, duration) the effects of rifaximin and placebo occur. The data will be evaluated by graphical display without rigorous statistical testing. The weekly logs will also record drug compliance. Bacterial quantity and content in stool along with presence of SBIO will also be assessed in secondary analysis. These are both exploratory analyses.

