10.1 EVALUATION DURING TREATMENT/INTERVENTION

Pre-treatment intervention & evaluation all undertaken in an outpatient clinic (day 0)

- MSKCC BFI (for all patients)
- Breath test (for patient volunteers)
- Stool Sampling (for patient volunteers)

Treatment with 400 mg rifaximin bid x 4 weeks or placebo bid x 4 weeks.

Post treatment evaluation at an outpatient clinic, for those patients who volunteered for extra testing. (days 26 - 35 and days 53 – 63)

- MSKCC BFI
- Breath test
- Stool Sampling

Post treatment evaluation for patients not volunteering for extra tests which can be undertaken in the patients home during the following periods. (days 26 - 35 and 53 – 63)

- **MSKCC BFI**

All patients will be required to fill out a weekly stool log/diary for the duration of the trial. There are questions in the log/diary to assess patient compliance also.

One to twenty-four months following completion of the phase III trial patients will be offered a 3 week course of metronidazole. They will then be assessed again using the BFI at pretreatment and at 0-1 and 4-6 weeks post-treatment. (21-30 days and 49 – 63 days following starting metronidazole)

MSKCC BFI

The MSKCC BFI is a validated instrument in the assessment of bowel function following rectal cancer surgery over a 4 week period.[5] It consists of 18 items to which patients respond using a 5-point Likert scale, ranging from Always to Never. There is a summary score, and three subscales with good internal consistency (Frequency ($\alpha=0.75$), Dietary ($\alpha=0.78$), Urgency ($\alpha=0.79$)) and test-retest reliability (total score =0.84, Frequency=0.74, Dietary=0.62, Urgency=0.87). The instrument has demonstrated discriminant and construct validity. It is written at a grade 8 reading level, and takes 5-10 minutes to complete. The BFI if filled out at home can be emailed or mailed back to the investigator where they will be stored on a secure database and a locked drawer. Should there be any incomplete or ambiguous answers a follow up phone call will be made by one of the consenting physicians to clarify the answer. However in a prior trial by the Co-PI ([name] 06-151), of the 125 patients who answered the BFI on multiple occasions less than 5 items per question were missing or filled out inadequately.

Breath Test

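### The primary score (global BFI) is declared missing when a single item that does not enter it is left unanswered

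*Combined protocol and SAP*

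**What the plan says.** All the scoring rules are in Section 14.0.

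- Global score: "A global score will be calculated by adding the subscale scores". No single item enters it.
- Total score: "An additional aggregate score (total score) will also be calculated with the subscales and the single items". The sentence reporting development data shows that there are four single items: "The average total score (frequency, urgency, dietary, plus four single items".
- Missing rule: "The global score will be considered missing if any of the subscales or single items were missing". The total score has no missing rule of its own.
- Substitution of missing items by a mean applies only within a subscale. Nothing is provided for a missing single item.
- Role of the global score: the main comparison is the change in global BFI from baseline to 4 weeks, analysed by ANCOVA with week-4 BFI as outcome and baseline BFI as covariate. For sample size, "Power calculations are based on the global score on the BFI".

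Section 10.1 adds a safeguard. For "any incomplete or ambiguous answers a follow up phone call will be made by one of the consenting physicians to clarify the answer".

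**The concern.** The missing rule makes the global score depend on four items that its definition leaves out. The single-item condition fits the total score, which is the score that contains those items and has no rule of its own.

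Because the ANCOVA needs the score at both visits, a patient has eight chances (four items, two visits) to be lost for a reason unrelated to the endpoint. The rule is also uneven. A patient may leave several subscale items blank and stay in through mean substitution, while one blank item outside the score puts a patient out.

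Two things are at stake: avoidable exclusions in a trial sized for 60 analysed patients, and a choice between two conflicting sentences that might otherwise be made after results are visible.

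**Working it through.** **1. The texts side by side.** Let F, D and U be the frequency, dietary and urgency subscales and S1 to S4 the single items.

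- Global = F + D + U.
- Total = F + D + U + S1 to S4.
- Global is missing if any of F, D, U, S1, S2, S3 or S4 is missing.

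The third line is not needed to compute the first. With F, D and U valid, the global score can always be calculated.

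**2. The plan's power.** Inputs from Section 14.0: difference 5.8, SD of change 8, 30 per arm, two-sided 5%.

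- Noncentrality: 5.8 / (8 × √(2/30)) = 2.81.
- Power: 80.2% by the normal approximation and 78.8% by the exact noncentral t.

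The stated 80% is reproduced and is not in dispute.

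**3. Size of the avoidable loss.** Assumptions: each single item stays unanswered after the call with probability q, the same at both visits, and items are independent. The documents do not give q, so a range is shown.

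- Share of patients lost = 1 − (1 − q)^8.
- Remaining per arm = 30 × (1 − q)^8.
- t-test power uses SD 8.
- ANCOVA power uses a residual SD. With score SD s at both visits and SD of change 8, the correlation is ρ = 1 − 64/(2s²) and the residual SD is s√(1 − ρ²). At s = 8, ρ = 0.50 and the residual SD is 6.93. Degrees of freedom are N − 3.

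| q | Loss | Of 60 patients | Left per arm | t-test power | ANCOVA power (s = 8) |
|---|---|---|---|---|---|
| 0 | 0% | 0 | 30.0 | 78.8% | 89.0% |
| 0.4% | 3.2% | 1.9 | 29.1 | 77.5% | 88.0% |
| 1% | 7.7% | 4.6 | 27.7 | 75.4% | 86.4% |
| 1.6% | 12.1% | 7.3 | 26.4 | 73.3% | 84.6% |

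**4. Sensitivity to the score SD.** The SDs quoted in Section 14.0 by type of anastomosis run from 7 to 9. At q = 1.6%, ANCOVA power is 88.2% for s = 7 and 82.2% for s = 9.

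**5. An outer bound.** Section 10.1 reports earlier experience with 125 patients, in a sentence that is hard to read. If it means fewer than 5 of 125 per item, the ceiling is 4%. With no answer recovered by phone and the same rate at both visits, the loss would be 1 − 0.96^8 = 27.9%, with t-test power 64%. That is a limit under unfavourable assumptions, not an expectation. If missing items cluster in the same patients, the loss is smaller at every q.

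**The case against.** The strongest reply accepts the mismatch and disputes its weight.

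- **ANCOVA is the planned analysis, and its power stays above 80% over the assumed range of 0.4% to 1.6%.** This stands. The t-test column matters only because the plan used that test for sizing.
- **The loss may be smaller still.** Baseline forms are completed in clinic, and so are week-4 forms for the extra-testing volunteers, hoped to be half the patients. If clinic forms were always complete (an assumption; the plan states no check), only half the patients would be exposed, at one visit. The loss is then 0.5 × (1 − (1 − q)^4) = 0.8%, 2.0% or 3.1%, about 0.5, 1.2 or 1.9 of 60 patients, and ANCOVA power is at least 88.0%. This is a fair lower scenario.
- **Recruiting 35 per arm gives slack.** A 12.1% loss from 35 leaves 35 × 0.879 = 30.8. However, Section 14.0 sets that margin aside for dropout, so it covers this loss only if dropout is low.
- **The likeliest explanation is a slip, with global written for total.** This is plausible, but the documents do not say so. The other reading, that the global score was meant to include the single items, would contradict its definition.

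These points limit the size. None of them makes the missing rule agree with the definition.

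**Conclusion.** The concern holds. As written, the rule discards primary scores that can be fully computed, so the sentence is wrong and not merely incomplete. The contradiction can be read directly from the text and does not depend on any assumed rate.

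Its practical effect is probably small to moderate. The losses of 2 to 7 patients in 60 rest on assumed residual rates of 0.4% to 1.6%, independence, equal rates at both visits, and a dropout margin already used up. Missing single items could occur in either arm and at either visit, so no direction of bias is claimed. It should be fixed because it decides who enters the primary analysis of a small trial and the correction is easy.

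**What to change.** In Section 14.0, replace the missing rule with two statements: the global score is missing only when at least one of the three subscales is missing; the total score is missing when a subscale or a single item is missing. Check this against the instrument's published scoring (reference 5), which the documents do not reproduce. If that scoring does put single items in the global score, the definition is what must change.

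While editing the paragraph, state what happens to a subscale with exactly half its items answered. Substitution applies "when >50 percent of the items in the subscale is completed", and "A subscale will be considered missing if more than one-half of the items are missing", so that case meets neither condition. This is a rare boundary case, and the main point does not rest on it.

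The cost is two or three sentences, settled before unblinding. No extra data are needed.

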Appendix 2. Patients will then be invited to undertake a hydrogen breath test and fecal

sampling to assess for bacterial content in their small intestine and stool. Following stratification of patients by the method of anastomosis (stapled or hand sewn), the patients will then be randomized into two groups. The patients will receive treatment with rifaximin or placebo depending on the arm of the trial to which they have been randomized. Patients will at this stage on a volunteer basis be asked to submit stool samples and undertake a breath test. Patients will receive the respective treatment for four weeks. Following cessation of treatment all patients will be assessed using the BFI and respective patients will have repeat stool sampling and breath testing. Patients will then have these tests repeated 4 weeks later. This corresponds to 8 weeks after the start of the trial. For those patients not undertaking stool and breath testing, they will be reminded by phone, mail or email to fill out the BFI. Before and during the trial patients will be asked to fill out a weekly stool diary to evaluate trends on bowel function.

Appendix 3. Both the patients and the physicians will be blinded to the patient treatments. The Initial consultation along with subsequent rounds of testing with submission of stool samples and breath testing will be undertaken by one of the consenting physicians at a specifically arranged and designated “research clinic” at one of MSKCC’s network centers. (Sleepy Hollow, Commack, Main Campus and 53rd St). Patients may also be seen and consented at their regular follow up colorectal clinic visits. At 1 – 24 months after completion of the phase III portion of the trial, patients will be contacted by phone and given the option of receiving metronidazole in a followup, single arm study in which all patients receive the antibiotic. Patients who wish to participate will be mailed a drug prescription for a 3 week course of metronidazole 500mgs tid as well as the BFI forms and stool diary. Pretreatment and posttreatment BFI scores will be collected and analyzed for change in bowel function as was done in the initial Phase III study.

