15.3 Randomization

This is a double blind randomized comparison of the antibiotic rifaximin and placebo in the treatment of bowel dysfunction following rectal resection for cancer. After eligibility is established and immediately after consent is obtained, patients will be registered in the Protocol Participant Registration (PPR) system and randomized using the Clinical Research Database (CRDB), by calling the MSKCC PPR Office at [contact] between the hours of 8:30 am and 5:30 pm, Monday - Friday. Randomization will

be accomplished by the method of random permuted block, and patients will be stratified by the variable of type of anastomosis (stapled or hand sewn). Since this is a double blind study, the patients' treatment assignments can be viewed in the CRDB only by the hospital pharmacists who are dispensing the study drugs.

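### The primary ANCOVA omits anastomosis type, the factor used to stratify randomisation, so the treatment standard error may be slightly too large

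*Combined protocol and SAP*

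**What the plan says.** Section 4.2 describes "stratification of patients by the method of anastomosis (stapled or hand sewn), the patients will then be randomized into two groups". Section 15.3 repeats the factor and specifies permuted blocks. Section 14.0 gives the reason for stratifying: "to ensure the two arms are balanced, as surgical procedure is known to correlate with BFI".

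The primary analysis, also in Section 14.0, is an "ANCOVA model, with baseline BFI and treatment indicator as covariates and 4 week BFI as the dependent variable". Anastomosis type is not in it, and no reason is given for leaving it out.

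Later in Section 14.0, under secondary analyses, the plan states that "we will examine the change in BFI scores adjusted for possible cofounders, such as peri-op radiotherapy". That list is open, so anastomosis type could be included, but it is not named and these analyses are not primary.

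The power statement does not use the ANCOVA. It is worded "Using a two-sided, two sample t-test" and rests on this input: "we assume that the standard deviation of the differences to be 8 and the average BFI score at baseline to be 44".

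**The concern.** Stratifying on a prognostic factor makes the arms more alike than simple randomisation would. The analysis reflects this only if the factor is in the model. If it is left out, the variation it explains beyond baseline BFI is counted as noise, and the model-based standard error describes a less balanced design than the one used.

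The plan itself treats the factor as prognostic. Section 14.0 reports mean scores of 42 (hand sewn) and 51.6 (stapled) in the development cohort, and 43.3 and 49.4 at 6 months in a prospective cohort. At stake are a slightly wide confidence interval and slightly reduced power for the primary comparison in a trial of about 60 analysed patients.

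**Working it through.** **The plan's own figure.** Inputs from Section 14.0: 30 per arm, SD of change 8, two-sided 5%, 80% power.

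- Normal approximation: (1.96 + 0.84) × 8 × √(2/30) = 5.79 points. Power at 5.8 points is 80.2%.
- Exact t: detectable difference 5.88 points. Power at 5.8 points is 78.8%.

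The stated 5.8 points at 80% reproduces. It refers to a t-test on change, so it does not depend on whether the ANCOVA contains the stratum.

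**Inputs for the effect of the omission.**

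- Gap between strata, g: 51.6 − 42 = 9.6, or 49.4 − 43.3 = 6.1 (Section 14.0). Both are cross-sectional. Assumption: the gap is the same at baseline and week 4.
- Within-stratum SD at each visit: assumed 8 (the documents give 7 to 9).
- Hand-sewn share, p: 36/117 = 31%, from the prospective cohort. This trial's share is not given.
- Baseline to week-4 correlation within stratum, r: not given. With SD 8 at each visit, the SD of change is 8 × √(2(1 − r)). This equals the plan's 8 at r = 0.5. The reported test-retest value of 0.84 serves as a high case, although it is for the total score and the model concerns the global score.

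**Formulas.** Let V = 8² + p(1 − p)g² be the variance at each visit and C = r × 8² + p(1 − p)g² the covariance between visits.

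- Residual variance without the stratum: V − C²/V.
- Residual variance with the stratum: 8²(1 − r²).
- Standard error ratio: the square root of the first over the second.

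**Worked case** (p = 0.308, g = 9.6, r = 0.5):

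- p(1 − p)g² = 19.6, so V = 83.6 and C = 51.6.
- Without the stratum: 83.6 − 51.6²/83.6 = 51.8. With it: 64 × 0.75 = 48.0.
- √(51.8/48.0) = 1.038, an excess of 3.8%.
- The gap left after baseline adjustment at r = 0.5 is g(1 − r), that is 4.8 points for g = 9.6 and about 3.1 for g = 6.1.

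**Range at 31% hand sewn:**

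| r | Implied SD of change | SE excess, gap 6.1 | SE excess, gap 9.6 |
|---|---|---|---|
| 0.3 | 9.5 | 2.9% | 6.1% |
| 0.5 | 8.0 | 1.8% | 3.8% |
| 0.7 | 6.2 | 1.0% | 2.1% |
| 0.84 | 4.5 | 0.5% | 1.0% |

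Only the r = 0.5 row agrees with the plan's SD of change of 8.

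**Other stratum mix.** If the assumed mean baseline of 44 reflects the quoted stratum means, the hand-sewn share is (51.6 − 44)/9.6 = 79% or (49.4 − 44)/6.1 = 89%. At r = 0.5 the excess is then 3.2% (79%, gap 9.6) or 0.9% (89%, gap 6.1). At r = 0.84 it is 0.8% or 0.2%.

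**Simulation** (10,000 trials per scenario, N = 60, permuted blocks of 4 within stratum as an assumed block size, r = 0.5, 31% hand sewn). Mean SE, SD of the estimate and type I error are from the runs with no treatment effect; power is from the runs with a 5.8-point effect.

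| | Gap 6.1, without | Gap 6.1, with | Gap 9.6, without | Gap 9.6, with |
|---|---|---|---|---|
| Mean model SE | 1.827 | 1.796 | 1.864 | 1.797 |
| True SD of estimate | 1.813 | 1.809 | 1.818 | 1.805 |
| Type I error | 4.8% | 5.0% | 4.3% | 4.8% |
| Power at 5.8 points | 88.2% | 89.0% | 86.2% | 88.0% |

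The mean estimate was about 5.8 in every run with that effect, so neither model is biased. The true spread of the estimate hardly differs between models. What changes is mainly the reported standard error.

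**The case against.** The strongest case against is that little is lost. Stratified randomisation already delivers nearly all the precision: the true SD of the estimate differs by less than 1% between the two models. The stated purpose of stratifying, balance between arms, is met without a model term. What remains is a slightly conservative test, and in the cases consistent with the plan's SD of change, power stays above 80%. This stands, and it makes the point minor.

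It is also fair that the key premise is not in the documents. Patients are 1 to 5 years past restoration of continuity (Section 6.2), and the plan assumes no change on placebo, so baseline BFI may carry much of the difference between strata. The figures above assume that the full gap persists, and the lower bound is zero. The 6.1% figure at r = 0.3 should carry little weight, because it implies an SD of change of 9.5 against the plan's 8.

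The open list of secondary adjustments is a weaker defence. Adjusting for anastomosis type there would leave the primary standard error, interval and p-value as they are.

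**Conclusion.** The point holds as a small one. The plan stratifies on a factor it considers prognostic and omits it from the primary model. On inputs consistent with the plan's SD of change (SD 8 per visit, r = 0.5) and with the gap persisting in full, the treatment standard error is overstated by 1.8% to 3.8% at 31% hand sewn, and by 0.9% to 3.2% at 79% to 89% hand sewn. Simulated power at 5.8 points is about 1 to 2 points lower at 31% hand sewn. At r = 0.84 the excess is at most about 1%. If anastomosis type adds nothing beyond baseline BFI, it is zero.

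The error is in the conservative direction, and the planned sample size does not rest on it. The correlation, the persistence of the gap and the trial's stratum mix are assumptions. The change is recommended because it aligns the analysis with the randomisation at almost no cost.

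**What to change.** In Section 14.0, specify the primary model as week-4 global BFI on treatment, baseline global BFI and anastomosis type (stapled or hand sewn). Do this before unblinding, since adding the term afterwards would be open to the charge of a data-driven choice.

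The cost is one sentence and one of 57 residual degrees of freedom, and the variable is already recorded at randomisation. If anastomosis type turns out not to predict week-4 BFI, the loss is negligible: at r = 0.5 the simulated standard error is 1.796 with or without the term, and the detectable difference moves only from 5.098 to 5.100 points. The sample size and the 5.8-point design figure can stay as they are.

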2.3 Secondary objectives

- To determine if reduction in intestinal bacterial quantity correlates with improvement in bowel symptoms (BFI score).
- To explore the bacterial composition of stool before and after antibiotic treatment.
- To identify dynamic changes in bowel function during and after antibiotic treatment using a bowel function log.
- To identify the efficacy of metronidazole in the treatment of bowel dysfunction as measured by the MSKCC BFI in patients following AR or SPS for rectal cancer for patients who have no improvement following treatment with rifaximin or placebo.

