Methane and hydrogen breath testing is currently the best non-invasive way of assessing small bowel bacterial overgrowth.[22] The test takes 1 hour and can be taken in the outpatient clinic. The patient must fast at least 12 hours prior to starting the test. The patient takes a baseline breath and exhales into a container. He/she then ingests a quantity of lactulose. If there is overgrowth of bacteria in the small intestine the sugar is not absorbed but is instead fermented by the bacteria in the gastrointestinal tract producing hydrogen and methane. The human body does not endogenously produce either of these gasses. These gasses can then be detected in the breaths of patients indicating bacterial overgrowth in the small bowel. Subsequent breaths are then taken at varying intervals up to 90 minutes from the initial ingestion of the sugar and are assessed for methane and hydrogen levels. The samples will be analyzed at Metabolic Solutions Incorporated®, a commercial laboratory.

Stool Sampling

Memorial Sloan Kettering Cancer Center
[name]
[name]

Stool samples will be taken during the outpatient visits. Patients can submit a sample by defecating into a container or a sample can be taken by gentle rectal examination. The samples will be collected in the outpatient setting and frozen at -80 degrees Celsius. DNA will be extracted using commercial kits (Qiagen®). Bacterial culture has proven to be unreliable as a quantitative measure of fecal content as only a tiny minority of fecal bacteria will survive in culture. As such we plan to quantify fecal bacteria using real time quantitative PCR for the gene for 16s ribosomal RNA as previously described.[23] This gene is present in all bacteria and has both conserved and variable domains. For quantification of total fecal bacteria, PCR primers amplifying the conserved domain will be used and the PCR product will be measured using the Syber Green method.

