12.0 CRITERIA FOR THERAPEUTIC RESPONSE/OUTCOME ASSESSMENT

The ultimate response to treatment with antibiotics for ARS will be with the MSKCC bowel function instrument. This is an 18 point questionnaire which takes about 10 minutes to complete. It can be completed either in the outpatient setting or at home. This instrument has been validated in the assessment of bowel function following rectal cancer surgery over a 4 week period.[5] The BFI score will be calculated by the consenting physicians.

The purpose of the correlative studies is to assess if symptoms of ARS, indicated by a reduced MSKCC bowel function instrument score are associated with increased bacterial content in the gastro-intestinal tract or with a specific pattern of bacterial colonization. To this end bacterial content in the small intestine will be assessed using the breath test and bacterial content and colonization patterns will be assessed from fecal stool samples.

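### The breath test enters the exploratory analysis only as SIBO present or absent, although gas levels are collected and the objective concerns bacterial quantity; its duration is also stated in two ways

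*Combined protocol and SAP*

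**What the plan says.** The first secondary objective (Section 2.3) reads: "To determine if reduction in intestinal bacterial quantity correlates with improvement in bowel symptoms (BFI score").

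Section 12.0 gives the small-bowel part of this to the breath test: "bacterial content in the small intestine will be assessed using the breath test". No other small-bowel measure is planned. Section 10.1 says that the breath samples "are assessed for methane and hydrogen levels", so the raw result is a series of quantities. For stool, the same section says "we plan to quantify fecal bacteria using real time quantitative PCR for the gene for 16s ribosomal RNA".

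The analysis text in Section 14.0 is one sentence, "Bacterial quantity and content in stool along with presence of SBIO will also be assessed in secondary analysis", followed by "These are both exploratory analyses". (SBIO is taken to mean SIBO.) The text names no model and no test for these data, and gives no threshold for calling a breath test positive.

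On the conduct of the test, Section 10.1 says "The test takes 1 hour and can be taken in the outpatient clinic" and, a few lines later, "Subsequent breaths are then taken at varying intervals up to 90 minutes from the initial ingestion of the sugar".

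Section 7.0 hopes that half of each arm will volunteer for stool and breath testing.

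**The concern.** The objective is about a change in amount, and the variable named for the breath test is a category. Section 6.2 does not require SIBO at entry, so some volunteers may be negative at baseline, and on a yes/no scale they cannot show a reduction. A volunteer whose gas levels fall but stay above the cut also counts as unchanged. Any association between small-bowel bacteria and BFI improvement is therefore weakened by the choice of variable, in a group that is already small. Because no threshold is stated, the yes/no variable itself is undefined and could be settled after the data are seen.

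The two statements on duration add a question of standardisation. A test that ends at 1 hour cannot include a breath at 90 minutes, and no sampling times are listed that would settle which span applies at each of the three visits.

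**Working it through.** **The plan's own figure.** The only power statement is for the primary BFI comparison (Section 14.0): difference 5.8, SD 8, 30 per arm, two-sided 5%. Here 5.8 / (8 × √(2/30)) = 2.808, and Φ(2.808 − 1.96) = 0.802 (0.788 with the exact t distribution). The stated 80% is reproduced. It does not depend on the breath test, for which the plan gives no figure.

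**Number of volunteers.** Half of 60 analysable is 30; half of 70 recruited is 35.

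**One measurement.** Let a normally distributed marker be cut so that a share p is positive, and let φ be the normal density at the cut. The share of information retained is φ² / [p(1 − p)].

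- p = 0.5: 0.3989² / 0.25 = 0.637, so 36% is lost.
- p = 0.2: 0.2800² / 0.16 = 0.490, so 51% is lost.
- p = 0.1: 0.1755² / 0.09 = 0.342, so 66% is lost.

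The loss exceeds one half only if p is below about 0.21 or above about 0.79.

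**Change between two visits, which the objective needs.** Let r be the correlation between the two measurements, with the same cut and the same p at both visits. Let p₁₁ be the probability of being positive at both. The squared correlation between the continuous change and the change in presence is φ²(1 − r) / (p − p₁₁). With r = 0 this reduces to the formula above. Two worked cases at r = 0.7:

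- p = 0.5, p₁₁ = 0.3734: 0.3989² × 0.3 / 0.1266 = 0.377, so 62% is lost.
- p = 0.1, p₁₁ = 0.0468: 0.1755² × 0.3 / 0.0532 = 0.174, so 83% is lost.

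Information lost by using change in presence:

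| Share positive | r = 0 | r = 0.3 | r = 0.5 | r = 0.7 |
|---|---|---|---|---|
| 50% | 36% | 45% | 52% | 62% |
| 30% | 42% | 51% | 58% | 67% |
| 20% | 51% | 59% | 65% | 73% |
| 10% | 66% | 73% | 77% | 83% |

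A simulation with 20,000 runs per setting agrees with this table.

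**What this means for power.** If the true correlation between breath change and BFI change were 0.5 (an assumption), a two-sided 5% test would have power of about 0.83 with 30 volunteers and 0.88 with 35 on the continuous scale. On change in presence it would have 0.19 to 0.61 and 0.22 to 0.68 over the same grid.

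**Duration.** 90 − 60 = 30 minutes separate the two statements in Section 10.1. The documents give nothing from which to put a figure on information lost through this.

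**The case against.** The strongest reply is that the objective already has a quantitative measure. The same volunteers give stool, total fecal bacteria are quantified by PCR, and Section 14.0 keeps that quantity. This stands. A reader might infer that most of the information from the 30 to 35 volunteers is lost, or that they are worth only a fraction of their number. The documents do not support that: the stool measure is unaffected, and even for a single breath measurement the loss passes one half only at prevalences that the plan does not state. Stool does not, however, stand in for the small bowel, which Section 12.0 measures separately.

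Second, Section 14.0 is a one-sentence summary. It does not forbid use of the levels, which will exist in any case. This also stands: the gap may be under-specification rather than a settled decision to dichotomise, and nothing is lost beyond recovery. The remedy is the same on either reading.

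Third, a reader might infer that a null SIBO result would be held against the bacterial theory. Section 3.0 states that theory chiefly in terms of fecal bacteria, which the stool PCR addresses directly, so a null breath result alone would not settle it.

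Fourth, a reader might infer that sampling times will differ between one patient's three tests. The wording can equally mean unequal spacing within a single test, and one commercial laboratory analyses all samples. What remains is the conflict between 1 hour and 90 minutes.

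Finally, the plan does not say that any particular gas summary tracks bacterial load. That is a reason to choose one with the laboratory and state it, not to leave the levels unused.

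**Conclusion.** The point holds in a limited form and is minor. As written, the planned analysis leaves unused about 36% to 83% of what the breath test can say about change between visits. That range assumes normally distributed gas values (possibly after transformation), the same share positive at both visits, between 10% and 50% positive, and a pre-post correlation between 0 and 0.7. None of these comes from the documents, and values outside them would move the range. The loss lies in the analysis plan and not in the data, and it concerns one exploratory measure in a voluntary subset. The primary BFI comparison and its sample size are unaffected. The two durations in Section 10.1 contradict each other whatever view is taken of the dichotomy.

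**What to change.** In Section 14.0, name one continuous summary of the hydrogen and methane levels, for example peak rise over baseline breath or area under the curve, chosen with the laboratory before unblinding. Analyse its change from the pretreatment test to each follow-up test, compared between arms and related to BFI change over the same interval. Keep SIBO presence as a descriptive line with its threshold stated. The analyses can stay labelled exploratory.

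In Section 10.1, reconcile the two statements of duration and list one set of sampling times, the same at all three visits.

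The cost is a few sentences and slight extra analysis work on data already collected. If visits are now booked for 1 hour and the longer span is the one kept, each test visit may take about 30 minutes more.
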